## **THE EFFECT OF MUSIC DURING NON-STRESS TESTING ON WOMEN'S COMFORT, VITAL SIGNS AND ANXIETY: A RANDOMIZED CONTROLLED STUDY**

Music has direct and indirect positive effects on the mother and fetus during pregnancy and perinatal period. This study was aimed at investigating effects of music played during the Non-Stress Test (NST) procedure on the mother's comfort, vital signs and anxiety.

The present study is a randomized controlled experimental study. Pregnant women who presented to the NST outpatient clinic of a research hospital in the Central Anatolia region of Türkiye between June 2025 and August 2025 comprised the population of the study. The study's sample size was calculated using the G\*Power 3.1.9.2 software based on data from a study by Baskurt and Yilmaz [1]. The mean anxiety scores and standard deviation values from that study were used, and the effect size was calculated as 0.79. The minimum number of pregnant women to be included in the sample of this study was calculated as 70 pregnant women, 35 in each group, using the G\*Power 3.1.9.2 software, based on an effect size of 0.79, an alpha value of 0.05, and a power value of 0.95. To increase the analysis power of the study, the study sample consisted of 173 pregnant women (music group= 93 and control group= 80).

The inclusion criteria of the study were as follows: being between the ages of 18 and 45 years, having completed the 32nd week of gestation, not having any risk factors in their pregnancy (such as premature rupture of membranes, preeclampsia, gestational diabetes), not having multiple pregnancies, not having low (80/60 mmHg and below) or high (140/90 mmHg) blood pressure levels, having eaten at least two hours before the NST procedure, not smoking or consuming alcohol at least two hours before the NST procedure, being able to communicate, not having any hearing problems, and volunteering to participate in the study.

The exclusion criteria of the study were as follows: Pregnant women who had a fetus with fetal distress, for whom emergency intervention was considered by the physician, who had impaired NST and required immediate intervention, who had a psychiatric disease diagnosis and hearing impairment were not included in the study (Figure 1).

**Figure 1.** CONSORT flowchart

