### *Data collection:*

The data of the study were collected from the pregnant women using the face-to-face interview technique at the NST outpatient clinic on the days and hours when the researcher was present in the hospital. The participating pregnant women were not informed of the group they belonged to. Since only the researcher knew the participants' groups, single-blindness was achieved in the study.

*Music Group:* The purpose of the study was explained to the pregnant women who met the inclusion criteria. After their written consent was obtained, they were administered the Personal Information Form, Prenatal Comfort Scale, Vital Signs Form, and State Anxiety Scale used to measure their anxiety level before the NST procedure. They were asked to lie on their left or right side. After the pregnant women were positioned, while the NST procedure was implemented they listened to music for 20-30 minutes. The pregnant women listened to the music on an MP3 player during the application. The duration of the music recorded on the

MP3 player was 30 minutes. To avoid hygiene problems, each pregnant woman was provided with individual headphones, which were given to them as a gift after the procedure. The volume of the music was adjusted by the pregnant women. After the procedure was completed, the Prenatal Comfort Scale, Vital Signs Form and State Anxiety Scale were administered again.

*Control Group:* The purpose of the study was explained to pregnant women who met the inclusion criteria. After their written consent was obtained, they were administered the Personal Information Form, Prenatal Comfort Scale, Vital Signs Form, and State Anxiety Scale used to measure their anxiety level before NST. They were asked to lie on their left or right side. They underwent no other intervention during the NST procedure. After the procedure was completed, the Prenatal Comfort Scale, Vital Signs Form and State Anxiety Scale were administered again.

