### ***Data Collection Tools***

*Personal Information Form:* The form was administered to determine the participant's socio-demographic characteristics such as age, education level, employment status, family type, income level, and her obstetric characteristics such as whether her pregnancy was planned, what her gestational age was and whether she had undergone NST before.

*Prenatal Comfort Scale (PCS):* Takeishi et al. developed the PCS to determine the prenatal comfort level of the woman in Japan in 2011 [4]. In the first version, the PCS had 34 items, but then they revised it and shortened to 15 items [5]. The short version of the PCS consists of 15 items and the following 5 subscales: "The impact of developing relations with the spouse on the paternity role - Husband" (3,4,7,9), "Interacting with the movements of the fetus - Fetus" (13,14), "Social support received from the people around - People" (11,12,15), "Acceptance of the maternal role and attachment to the baby-Mother" (1,5,8), "Realizing the changes in oneself during pregnancy-Myself" (2,6,10). Response given to the items are rated on a six-point Likert type scale ranging from 0 to 5 (0 = Strongly disagree, 1 = Disagree, 2 = Undecided, 3 = Somewhat agree, 4 = Agree, 5 = Strongly agree). The minimum and maximum possible scores that can be obtained from the PCS are 0 and 75, respectively. The higher the score is the higher the comfort level is. Şenol, Özkan and Aslan performed the validity and reliability study of the Turkish version of the PCS (2020), the Cronbach's alpha value of the PCS was 0.815 in Şenol, Özkan and Aslan's study [6].

*Vital Signs Form:* The form was used to record the pregnant women's body temperature, pulse rate, respiration rate and blood pressure values.

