*State Anxiety Scale (SAS):* Spielberger et al. developed the SAS to determine how an individual feels at a certain moment and under certain conditions (1983). Öner and Le Compte performed the validity and reliability study of the Turkish version of the SAS (1998) [7,8]. Some of the items are reverse scored. While the reverse scored items question positive emotions, the other items question negative emotions. Responses given to the items are as follows: "not at all" (1), "somewhat" (2), "moderately" (3), "very much" (4), which indicate the degree of severity of the feelings, thoughts or behaviors. In this section, items 1, 2, 5, 8, 10, 11, 15, 16, 19 and 20 are reverse scored. To calculate the total score of the SAS, the total score of the reversed items is subtracted from the total score of the non-reversed items. Then, 50 points, which is the constant value of the state anxiety scale, are added to this score. The result is the score for the overall SAS. The total score varies between 20 and 80. The higher the score is the higher the level of the anxiety is. While a score ranging between 0 and 19 indicates "no anxiety", a score ranging between 20 and 39 indicates mild anxiety, a score ranging between 40 and 59 indicates moderate anxiety, a score ranging between 60 and 79 indicates severe anxiety, and a score of 80 indicates very severe anxiety (Panic) [8].

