### ***Statistical Analysis of the Data***

The data obtained in the present study were analyzed using the SPSS (Statistical Package for Social Sciences) 25.0. In the analysis of the data, to compare the homogeneity between the groups, cross tables were created for categorical variables, and the Chi square ( $\chi^2$ ) and Fisher's exact test were used. Numerical variables were given as mean $\pm$ standard deviation ( $X \pm SD$ ) whereas categorical variables were given as number (n) and percentage (%). For non-parametric data that were not normally distributed, the Mann-Whitney U test was used to evaluate the difference between two groups, and the Kruskal-Wallis H test was used to find differences between the variables with three or more categories. Spearman correlation analysis was performed to reveal the relationship between the dependent variables. The Wilcoxon test (significance test of the difference between two paired groups) was used to test the difference in the dependent groups at two different measurement times. The significance level was accepted as  $p<0.05$ . The confidence interval was 95%.

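### No outcome is named primary in these documents and every test uses an unadjusted 0.05 level, so the chance of at least one false music effect is about 11–30%, depending on assumed correlations

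*Combined protocol and SAP*

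**What the plan says.** The title and aim give three outcome domains side by side, "COMFORT, VITAL SIGNS AND ANXIETY", without ranking them. The sample-size paragraph of the study description takes its effect size of 0.79 from anxiety data in a cited study: "The mean anxiety scores and standard deviation values from that study were used". It derives a minimum of 70 women (35 per group) and then reports a sample of 173, "music group= 93 and control group= 80".

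Under Data collection, both arms complete the instruments before the non-stress test (NST), and afterwards "the Prenatal Comfort Scale, Vital Signs Form and State Anxiety Scale were administered again". Under Data Collection Tools:

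- The vital signs are "body temperature, pulse rate, respiration rate and blood pressure values".
- The Prenatal Comfort Scale (PCS) has a total score and "consists of 15 items and the following 5 subscales".
- The SAS gives one total: "The result is the score for the overall SAS".

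Statistical Analysis of the Data names chi-square, Fisher, Mann-Whitney, Kruskal-Wallis, Spearman and Wilcoxon tests and closes with a single rule, "The significance level was accepted as" p<0.05. It does not list which variables receive a between-group test. It does not call any outcome primary or secondary, and it states no correction, order or gate.

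**The concern.** A 5% level limits the error of one test. When several outcomes are each tested at 5% and any of them may support the conclusion that music works, the chance of at least one false conclusion is larger.

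The plan leaves that route open in two situations:

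- **Music does nothing.** Anxiety may be non-significant while pulse, pressure or comfort crosses 0.05 by chance. Nothing in the text stops that result from being presented as a music effect.
- **Music helps anxiety only.** This is close to the case the trial was sized for. A false finding on comfort or a vital sign can then be added to a true finding on anxiety.

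At stake is how a reader should weigh an isolated significant result on any outcome other than anxiety.

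**Working it through.** **Inputs from the documents.** Level 0.05 per test (Statistical Analysis of the Data); effect size 0.79, power 0.95, minimum 70, final groups 93 and 80 (study description); instruments (Data collection, Data Collection Tools).

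**Assumptions.** Two-sided tests, because sidedness is not stated. The outcome count is inferred: SAS total, PCS total, temperature, pulse, respiration and blood pressure make 6, or 7 with systolic and diastolic separate. A common correlation ρ of 0, 0.5 or 0.9 is assumed, because the documents give none.

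**Step 1: the plan's own figure.** Per group, n = 2(z_α + z_β)²/d².

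- One-sided: 2(1.645 + 1.645)²/0.79² = 34.7, so 35 per group and 70 in total. This matches the plan.
- Two-sided: 2(1.960 + 1.645)²/0.79² = 41.6, so 42 per group and 84 in total. This does not match.

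So the 70 is the size for one test on one outcome, anxiety, and it agrees with a one-sided calculation. The final 173 exceeds either figure.

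**Step 2: music has no effect on anything.** With independent outcomes, P(at least one false) = 1 − 0.95^k:

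- k = 6: 1 − 0.735 = 26.5%
- k = 7: 1 − 0.698 = 30.2%

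With common correlation ρ, P = 1 − ∫ φ(u)[Φ((1.96 − √ρ·u)/√(1−ρ)) − Φ((−1.96 − √ρ·u)/√(1−ρ))]^k du, integrated numerically.

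| Outcomes | ρ = 0 | ρ = 0.5 | ρ = 0.9 |
|---|---|---|---|
| 6 | 26.5% | 20.7% | 10.8% |
| 7 | 30.2% | 23.0% | 11.4% |

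A Mann-Whitney simulation with 93 and 80 women, seven outcomes and assumed mixed correlations (systolic–diastolic 0.7, comfort–anxiety −0.4, others 0.1) gave 28%.

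The part of this in which SAS itself is not significant is the tabulated value minus 5 points: 21–25% at ρ = 0, 16–18% at 0.5 and about 6% at 0.9.

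**Step 3: music affects anxiety only.** The false claim must now fall among the other 5 or 6 outcomes. The formulas are the same, with k = 5 or 6.

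| Other outcomes | ρ = 0 | ρ = 0.5 | ρ = 0.9 |
|---|---|---|---|
| 5 | 22.6% | 18.3% | 10.2% |
| 6 | 26.5% | 20.7% | 10.8% |

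**Step 4: what controls the error.** Take SAS at 0.05 and Holm over six secondary outcomes, with no true effects.

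- No gate: at ρ = 0, 1 − 0.95 × (1 − 0.05/6)^6 = 1 − 0.95 × 0.951 = 9.7%. Simulation with 1,000,000 draws gave 9.7%, 8.1% and 5.3% at ρ = 0, 0.5 and 0.9.
- Secondary claims allowed only after a significant SAS result: 5.0% at all three, because every false claim then requires a false SAS result.

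In the anxiety-only case the gate is almost always open, and it is Holm that limits false secondary claims to 5%.

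**Step 5: power with 93 and 80 women (two-sample t approximation).**

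- SAS, d = 0.79 at 0.05: 99.9%.
- Secondary outcome, d = 0.5: 90% at 0.05 and 73% at the strictest Holm step, 0.05/6 = 0.0083. For Mann-Whitney at relative efficiency 0.955, about 89% and 70%.
- Difference detectable with 80% power: 0.43 SD at 0.05 and 0.54 SD at 0.0083.

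**The case against.** **Anxiety is the evident primary.** It sizes the trial, and a single SAS comparison keeps its 5% error. Both statements are true. A reader might infer from the heading that the SAS test itself is inflated; the documents do not support that. But supplying a sample-size input is not a commitment to judge the trial on that outcome, and the text makes no such commitment.

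**Comfort, vital signs and anxiety are separate questions.** Read that way, each keeps 5% and no correction is required by convention. This stands as far as it goes. The plan does not adopt that reading or confine its conclusions to it. Equally, it nowhere says that one significant result establishes a general benefit. The concern is that such a claim is left open, not that it is announced.

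**The headline range rests on assumptions.** This also stands. The count is inferred. The 11% end needs a correlation of 0.9 among measures as different as temperature, respiration and comfort, which nothing in the documents supports. The 30% end needs full independence, although all measures come from the same women at one visit. The rate exceeds 5% at every correlation examined.

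**The analysis is already reported as done.** The section is in the past tense and the 93/80 split is a realised one. A reader might infer that results steered the choice of outcome. The documents do not show when any rule was fixed, so that inference is unsupported. The timing does mean that disclosure comes before any new wording.

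**Conclusion.** The concern holds for the set of claims, not for the SAS test alone. Following the stated rule over the six or seven inferred outcomes gives an overall false-claim rate two to six times the nominal 5% if music has no effect, and two to five times among the remaining outcomes if it helps anxiety only. The figures assume two-sided between-group tests of total scores and a common correlation between 0 and 0.9. They leave out the five PCS subscales and the Wilcoxon, Kruskal-Wallis and Spearman tests. With the subscales added (11 or 12 outcomes) the rate at correlation 0 would be 43–46%, but the plan does not say that they are tested between groups, so that larger figure should not be read as the plan's rate.

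A reader might also infer that naming SAS as primary is enough. It is not: if the other outcomes are still claimed at 0.05, the rates in the working are unchanged.

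The finding is limited to these documents; an outcome may be designated elsewhere. The change should be made, but the omission does not invalidate the anxiety comparison.

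**What to change.** **First, disclosure.** Unless the rule was fixed before results were seen, the report should say that the primary outcome was designated post hoc, on the basis of the sample-size calculation, and that 5% overall error is not guaranteed.

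**Then state the hierarchy.** The single primary outcome is the between-group comparison of post-NST SAS total, two-sided 0.05. The statement should also name the test and say how the pre-NST score is used, since SAS is measured twice. For PCS total, temperature, pulse, respiration, systolic and diastolic pressure, choose one option:

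- (a) exploratory, with no claim of a music effect; or
- (b) claimed only after a significant SAS result, with Holm over the six tests (smallest step 0.0083).

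PCS subscales and the within-arm Wilcoxon, Kruskal-Wallis and Spearman results are exploratory. Naming SAS controls the error only together with (a) or (b).

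**Cost.** There are no extra participants or measurements, and the primary loses no power (99.9% at d = 0.79). Under (a), nothing can be claimed for comfort or vital signs. Under (b), nothing can be claimed for them if SAS is null, and at the strictest Holm step power for a 0.5 SD secondary difference falls from 90% to 73%.
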